##### **4.2 Data Management:**

Secure EDC system with role-based access

AES-256 encryption for all electronic records

#### **5. Ethical Protections**

##### **5.1 Confidentiality Measures:**

De-identified data storage,

Restricted access to research team members,

Publication protocols excluding identifiable information.

##### **5.2 Participant Safeguards:**

Voluntary participation with withdrawal option,

Dedicated research contacts for concerns,

Referral pathways for requested support services.

### **5.3 Special Population Protections:**

- Dual consent process for minor participants (assent + guardian consent),
- Age-appropriate communication protocols.

## **III. Participant Recruitment**

### **Sample Size:**

100,000-200,000 eligible households nationwide.

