### **3.2 Study Population:**

Registered patients (N=100,000-200,000) aged 18-60 years with:

Diagnoses of schizophrenia, bipolar disorder, paranoid disorder, schizoaffective disorder, epilepsy-related mental disorders, or intellectual disability with mental disorders;

Documented reproductive history (including live births, miscarriages, or preterm deliveries);

Residence in 10 representative regions (Shenyang, Changchun, Wuhan, Zigong, Mianyang, Suzhou, Beijing Haidian/Fangshan, Taiyuan, Xiamen).

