### **3.3 Data Collection:**

Electronic medical record extraction from national mental health registry

Community-based assessments via 686 Program network:

Household visits/telephone interviews conducted by trained mental health workers;

Structured questionnaire covering:

Marital/reproductive history,

Child developmental status,

Household socioeconomic indicators.

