#### **4. Data Analysis**

##### **4.1 Statistical Approach:**

Primary analysis: Descriptive statistics (SPSS 24.0)

Continuous variables: Mean (SD) or median (IQR) as appropriate

Categorical variables: Frequency distributions (%)

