### **Inclusion Criteria**

Patients diagnosed with schizophrenia, bipolar disorder, paranoid disorder, schizoaffective disorder, epilepsy-related mental disorders, or mental retardation with associated mental disorders, who are registered in the severe mental disorder management system, aged 18-60 years, and have a history of childbirth (including miscarriage, preterm birth, and full-term birth).

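### Does the plan need to change because its sample size is stated in both patients and households, minors are mentioned, and the child item has no stated unit?

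*Combined protocol and SAP*

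**What the plan says.** The range 100,000-200,000 appears twice with different nouns. Section 3.2 (Study Population) reads "Registered patients (N=100,000-200,000) aged 18-60 years with". Part III (Sample Size) reads "100,000-200,000 eligible households nationwide".

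Eligibility is written only for patients. The Inclusion Criteria in part III admit people "who are registered in the severe mental disorder management system, aged 18-60 years" with a "history of childbirth (including miscarriage, preterm birth, and full-term birth". The only exclusion is refusal. Nothing limits a household to one patient, and an eligible household is not defined.

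Section 5.3 nevertheless provides a "Dual consent process for minor participants (assent + guardian consent" and adds communication suited to age. No eligibility rule or target number for minors is given.

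The questionnaire topics in section 3.3 include "Child developmental status" and "Household socioeconomic indicators", with no respondent or recording unit. Section 4.1 is descriptive throughout. For counts it says "Categorical variables: Frequency distributions" with percentages, and it names no denominator.

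**The concern.** In a purely descriptive survey the percentages are the result, so the unit behind each one matters.

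- **Patients or households.** The two nouns give the same number only if every household contributes exactly one patient, which the protocol does not say.
- **Minors.** Nobody under 18 can meet the written criteria. If children take part, N omits them and their informant is undefined. If they do not, section 5.3 protects people the survey would not enrol.
- **Child item.** A patient may have several children. A figure per child, per parent with any affected child, or per enrolled patient would all fit the text. Patients whose only event was a miscarriage are eligible but have no child to assess.

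At stake is whether a policy reader could turn a published percentage into a number of children. Sampling error would not hide the ambiguity at this N.

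**Working it through.** **The plan's own figure.** The protocol gives no precision target, expected rate or response rate, so 100,000-200,000 cannot be re-derived. For scale, the simple-random-sample 95% half-width at p = 0.5 is 1.96 × √(0.25/N). This is 0.31 points at N = 100,000 and 0.22 points at N = 200,000.

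Every share used below is an assumption, because the documents give none.

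**1. Patients versus households.** Let k be the share of households with two eligible patients. Then patients = households × (1 + k).

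| k | 100,000 households | 200,000 households |
|---|---|---|
| 0.02 | 102,000 patients | 204,000 patients |
| 0.05 | 105,000 patients | 210,000 patients |
| 0.10 | 110,000 patients | 220,000 patients |

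The lower end stays inside the stated range and the upper end goes past it. The range is itself twofold wide and feeds no calculation, so nothing downstream alters.

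Weighting by patient instead of by household shifts a percentage by (2k/(1+k) − k) × D, where D is the difference in prevalence between two-patient and one-patient households. With D = 20 points:

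- k = 0.02: (0.0392 − 0.02) × 20 = 0.38 points
- k = 0.05: (0.0952 − 0.05) × 20 = 0.90 points
- k = 0.10: (0.1818 − 0.10) × 20 = 1.64 points

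With D = 0 the shift is zero. For the patient-level objectives in section 2, weighting by patient is correct, so there this is not a bias at all.

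**2. Minors.** With m enrolled minors per patient, total participants are N(1 + m). For m = 0.5 this is 150,000-300,000, and for m = 1 it is 200,000-400,000. These totals do not contradict the plan. The stated range counts patients in one place and households in the other, and in neither does it cap all participants.

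**3. Child item.** Suppose the item is yes/no, 10% of children are affected, siblings are independent, and 60/30/10% of parents have 1/2/3 children. The share of parents with any affected child is

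0.6 × 0.10 + 0.3 × (1 − 0.9²) + 0.1 × (1 − 0.9³) = 0.060 + 0.057 + 0.0271 = 0.1441.

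The same data therefore read 10.0% per child or 14.4% per parent. An 80/15/5 mix gives 12.2% and a 40/40/20 mix gives 17.0%. If siblings always agree, both readings are 10.0%.

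If a share c of patients without a living child stays in the denominator, the figure is 14.41% × (1 − c): 14.3% at c = 0.01, 13.7% at 0.05 and 13.0% at 0.10.

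**4. Reading the sections together.** Section 2, section 3.2 and the Inclusion Criteria all describe patients. The Procedures entry in part III identifies people through a registry, and what that registry holds is patients. Only the Sample Size entry says households.

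**The case for a change.** The strongest case for a change is the minors point combined with the child item. The wording on communication in section 5.3 suggests real contact with minors, section 3.3 collects child development, and the background motivates the survey by the number of children of affected parents. Under the assumptions above, a gap of about four points is many times the 0.2-0.3 point half-width, and a larger sample cannot remove it. Household and child-parent links are also hard to recover once interviews are over.

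Some of this stands. The protocol does not say whether children take part or are only described by a parent, and it names no denominator for child items.

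The rest is weaker:

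- Section 5.3 can be read as a standing safeguard that applies if a minor is ever approached. It adds protection and admits nobody. The questionnaire is not in the document and the consent pages were not available for this check. Those are the natural places for the informant and the recording unit.
- The four-point gap depends on independent siblings, a poor central case for children who share an affected parent. It also assumes a yes/no item, while section 4.1 allows a continuous summary too.
- Confusion for the reader would need a table published without its denominator.
- Links across households would add linkable family data at a scale of 100,000-200,000, under a plan that promises de-identified storage. The shift they would address is 0.4-1.6 points under assumed shares, and may be zero.

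**Conclusion.** No change to the plan follows. The household label is a clerical slip against a patient-based design, and it moves the count by 2-10% if that share of households holds two eligible patients. The section on minors leaves a question of wording with no statistical consequence: the range does not cap total participants, and no written criterion admits a minor.

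The child-item denominator is a gap that an analyst of a descriptive survey fills in the ordinary way: put all enrolled patients in the reproductive-history tables, leave patients without a living child out of the child tables, and label each percentage per child or per parent. The spread between readings, 10.0% against 12.2-17.0%, rests wholly on assumed prevalence, family sizes and sibling independence, and falls to nothing if siblings agree. No stated rule yields a wrong number, and household or child-parent linkage has no demonstrated gain.

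This judgement assumes that the tables will carry their denominators and that the questionnaire fixes the recording unit. Neither can be confirmed from the protocol text.

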### **Timeline:**

Projected commencement: February 2021

### **Procedures:**

- Registry-based identification via national mental health management system;
- Community outreach through 686 Program infrastructure.

### **Inclusion Criteria**

Patients diagnosed with schizophrenia, bipolar disorder, paranoid disorder, schizoaffective disorder, epilepsy-related mental disorders, or mental retardation with associated mental disorders, who are registered in the severe mental disorder management system, aged 18-60 years, and have a history of childbirth (including miscarriage, preterm birth, and full-term birth).

### **Exclusion Criteria**

Those who do not agree to participate in the survey.

## **IV. Risk-Benefit Assessment**

### **Potential Benefits:**

- Contribution to evidence-based policy development.
- Foundation for future intervention studies.

**Potential Risks:**

Minimal psychological discomfort during survey.

**Mitigation:**

Real-time withdrawal option,

Embedded support service referrals.

**Risk-Benefit Conclusion:**

Study procedures present minimal risk with significant potential to advance mental health service equity for vulnerable families.

